# 8.2.2 Suspected unexpected serious adverse reactions (SUSARs)

Adverse reactions are all untoward and unintended responses to an investigational product related to any dose administered.

Unexpected adverse reactions are SUSARs if the following three conditions are met:

- 1. the event must be serious (see chapter 8.2.1);
- there must be a certain degree of probability that the event is a harmful and an undesirable reaction to the medicinal product under investigation, regardless of the administered dose;
- 3. the adverse reaction must be unexpected, that is to say, the nature and severity of the adverse reaction are not in agreement with the product information as recorded in the Investigator's Brochure for an unapproved IMP or Summary of Product Characteristics (SPC) for an authorized medicinal product.

The sponsor will report expedited the following SUSARs through the web portal *ToetsingOnline* to the METC:

- SUSARs that have arisen in the clinical trial that was assessed by the METC;
- SUSARs that have arisen in other clinical trials of the same sponsor and with the same medicinal product, and that could have consequences for the safety of the subjects involved in the clinical trial that was assessed by the METC.

The remaining SUSARs are recorded in an overview list (line-listing) that will be submitted once every half year to the METC. This line-listing provides an overview of all SUSARs from the study medicine, accompanied by a brief report highlighting the main points of concern. The expedited reporting of SUSARs through the web portal *ToetsingOnline* is sufficient as notification to the competent authority.

The sponsor will report expedited all SUSARs to the competent authorities in other Member States, according to the requirements of the Member States.

The expedited reporting will occur not later than 15 days after the sponsor has first knowledge of the adverse reactions. For fatal or life threatening cases the term will be maximal 7 days for a preliminary report with another 8 days for completion of the report.

# 8.3 Annual safety report

In addition to the expedited reporting of SUSARs, the sponsor will submit, once a year throughout the clinical trial, a safety report to the accredited METC, competent authority, and competent authorities of the concerned Member States. This safety report consists of:

- a list of all suspected (unexpected or expected) serious adverse reactions, along with an aggregated summary table of all reported serious adverse reactions, ordered by organ system, per study;
- a report concerning the safety of the subjects, consisting of a complete safety analysis and an evaluation of the balance between the efficacy and the harmfulness of the medicine under investigation.

# 8.4 Follow-up of adverse events

All AEs will be followed until they have abated, or until a stable situation has been reached. Depending on the event, follow up may require additional tests or medical procedures as indicated, and/or referral to the general physician or a medical specialist.

#### 8.5 Monitoring

An external monitor will monitor the study and will assess (1) whether the rights and health of the subjects are protected, (2) whether data is correct and verifiable from source documents and (3) whether the study is in agreement with GCP, the approved protocol and legal requirements. A detailed monitor plan is added to this protocol.

#### 8.6 Data safety monitoring board (DSMB)

A DSMB is established to perform ongoing safety surveillance which means that (S)AEs will be monitored. The DSMB will have insight into the total number of (S)AEs and will, as needed, review individual records to be able to analyze potential associations between complications and the study protocol. The members will not have insight in the efficacy data. Accumulating data on (S)AEs will be send to the DSMB for safety review by the researchers. All members have independent positions from the trial study group. The composition and responsibilities of the DSMB are described in detail in the DSMB charter.

The advice(s) of the DSMB will only be sent to the principal investigators of the study. Should they decide not to fully implement the advice of the DSMB, they will send the advice to the reviewing METC, including a note to substantiate why (part of) the advice of the DSMB will not be followed.

#### ETHICAL CONSIDERATIONS

#### 9.1 Regulation statement

The study will be conducted according to the principles of the Declaration of Helsinki (seventh revision, October 2013) and in accordance with the Medical Research Involving Human Subjects Act (WMO).

#### 9.2 Recruitment and consent

Parents or caregivers of infants with known red blood cell alloimmunization that were monitored throughout pregnancy for anemia and were treated with IUT(s) for anemia, will be informed (verbally and in writing) about the study by the supervising neonatologist or a member of this research team. Parents can consider their decision at least 24 hours and can ask additional information or questions to an independent doctor before they are asked for their written consent. See appendix A and B (Patient information and Consent form).

#### 9.3 Benefits and risks assessment, group relatedness

HDFN is a condition limited to the neonatal population (group relatedness) Late anemia is a common complication of this condition during the first three months of life, currently treated with top-up transfusions. EPO could potentially be a less invasive alternative to top-up transfusions and be beneficial to our study subjects in terms of reducing the number of needed transfusions.

# 9.4 Compensation for injury

A liability insurance is obtained in accordance with article 7 of the WMO. This insurance covers:

 A maximum of €650.000,- for injury or death for each subject who participates in this study;

- A maximum of €5.000.000,- for injury or death for all subjects who participate in this study;
- A maximum of €7.500.000,- for the total damage for all subjects of studies by the same organization in each year of insurance coverage.

This insurance applies to the damage that becomes apparent during the study or within 4

years after the end of the study.

# 9. ADMINISTRATIVE ASPECTS AND MONITORING

# 10.1 Handling and storage of data and documents

Data management will be implemented according to Good clinical practice (GCP)-guidelines and will comply with the Dutch personal data protection act (Wbp). Data will be handled confidentially and anonymously by coding. The key to the code will be safeguarded by one of the investigators. The coded patient data will be entered in CASTOR (www.castoredc.com), a GCP conform internet based electronic data capture tool secured with login codes. Data will only be transferred encrypted. Data will be stored for 15 years according to the WGBO.

# **10.2 Monitoring and Quality Assurance**

The conduct of the study will be monitored, as is described in detail in the monitoring plan.

# **10.3 Amendments**

A 'substantial amendment' is defined as an amendment to the terms of the METC application, or to the protocol or any other supporting documentation, that is likely to affect to a significant degree:

- the safety or physical or mental integrity of the subjects of the trial;
- the scientific value of the trial;
- the conduct or management of the trial; or
- the quality or safety of any intervention used in the trial.

All substantial amendments will be notified to the METC and to the competent authority. Non-substantial amendments will not be notified to the accredited METC and the competent authority, but will be recorded and filed by the sponsor.

#### 10.4 Annual progress report

The investigator will submit a summary of the progress of the trial to the accredited METC once a year. Information will be provided on the date of inclusion of the first subject, numbers of subjects included and numbers of subjects that have completed the trial, serious adverse events / serious adverse reactions, other problems, and amendments.

#### 10.5 End of study report

The sponsor will notify the accredited METC and the competent authority of the end of the study within a period of 90 days. The end of the study is defined as the last patient's last visit. In case the study is ended prematurely, the sponsor will notify the accredited METC and the competent authority within 15 days, including the reasons for the premature termination. Within one year after the end of the study, the investigator will submit a final study report with the results of the study, including any publications/abstracts of the study, to the accredited METC and the Competent Authority.

# 10.6 Public disclosure and publication policy

The trial will be registered with European drug regulatory affairs clinical trials (EudraCT). Additionally, the trial will be registered with www.clinicaltrials.gov. Results of the study will be submitted for publication to a peer-reviewed international medical journals.

# **10. STRUCTURED RISK ANALYSIS**

# 11.1 Potential issues of concern

# a. Level of knowledge about mechanism of action

The mechanism of action of EPO in its currents indication is well known and detailed in the SPC, page 16. The use of EPO in a neonatal population with HDFN is further described in chapter 7, but overall seems safe with promising clinical results. In this population, affected fetuses are treated with IUTs. Blood transfusions, including IUTs, are known to enhance bone marrow suppression and suppress erythropoiesis. EPO could in turn stimulate erythropoiesis and reduce or treat anemia after birth.

# b. Previous exposure of human beings with the test product(s) and/or products with a similar biological mechanism

The effect of the exposure of human beings to darbepoetin alfa is well known as it is a registered product in the treatment of anemia in chronic kidney disease. In patients with HDFN, off-label and/or experimental use has been described with no serious adverse events.

# c. Can the primary or secondary mechanism be induced in animals and/or in *ex-vivo* human cell material?

The working mechanism of EPO and specifically of darbepoetin have been extensively studied in non-clinical settings.

# d. Analysis of potential effect

A lower dosage is used in anemic patients with chronic kidney disease (SMPC), supporting the probable effectiveness of this dosage to enhance erythropoiesis. A similar dosage has been administered before and much higher dosages have been safely used when the primary objective was neuroprotection, as EPO only partly crosses the blood-brain barrier.

#### e. Pharmacokinetic considerations

The half-life of darbepoetin alfa is longer than of recombinant human erythropoietin, justifying a less frequent administering for an equal biologic response. In adults with chronic kidney disease, the half-life is about 73 hours with subcutaneous injections. Pharmacokinetic research in pediatric patients (age 2 to 16 year) with chronic kidney disease, showed similar values (SPC page 19,20).

#### f. Study population

The study population is by its nature a vulnerable group, consisting of infants with HDFN. Standard procedure in our hospital is to admit neonates with HDFN to the high care unit, where they are clinically and biochemically (bilirubin, hemoglobulin) closely monitored and phototherapy treatment is started. Infants randomized to darbepoetin treatment will start treatment after the first week of life for a consecutive period of 8 weeks. All infants with HDFN are followed up to 3 months of age in an out-clinic setting.

#### g. Interaction with other products

No known interaction is known of darbepoetin alfa with other products (SPC page 12).

#### h. Predictability of effect

To evaluate the effect of darbepoetin administration, hemoglobulin levels will be carefully followed. National transfusion guidelines are followed to determine the need for top-up transfusion bases on hemoglobulin cut-offs.

#### 11.2 Synthesis

Good neonatal research is essential if to improve the care and outcome of newborns. The study has been designed to allow parents time to consider participation by approaching them timely for consent. The parents are under no obligation to join the trial and participation is

completely voluntary, as specifically stated in the parent information leaflet.

The results of this study are important to further optimize treatment of HDFN and reduce the transfusion need of this population. Darbepoetin alfa is an approved drug to treat or prevent anemia and did not give rise to any major safety concerns thus far. The study population is a vulnerable group as the patients are newborns, but this research cannot be conducted in another population. Apart from 8 subcutaneous injections with the study medication for half of the study population and an additional visit to assess development of the patients at the age of 2 years for all participants, there is no extra burden for participating infants.

## 1. Introduction

The EPO-4-Rh study is a single center randomized controlled trial to evaluate the role of darbepoetin alfa (a long acting agent of erythropoietin or EPO) in reducing the incidence of anemia in infants with hemolytic disease of the fetus and newborn (HDFN), treated with one or more intrauterine transfusion (IUT), compared to a control group of infants with HDFN without darbepoetin alfa treatment. The trial is registered with ClinicalTrials.gov, identifier NCT03104426.

The primary hypothesis is that treatment with EPO will reduce the number of postnatal transfusions per infant in a population of severe HDFN, which is defined by the need for intrauterine transfusion. Recruitment of patients started in October 2017.

## 2. Background

The mainstay of antenatal treatment of fetal anemia due to red cell alloimmunization is (serial) IUT. The mainstay of postnatal treatment in HDFN is (1) intensive phototherapy and, if necessary, exchange transfusion to treat hyperbilirubinemia and prevent kernicterus, and (2) postnatal transfusions to treat anemia. Up to 80% of infants with HDFN treated with IUT require at least one postnatal transfusion for anemia during the first 3 months of life, with a median of two postnatal transfusions involving two hospital admissions per infant. Postnatal anemia can be divided in early (up to 7 days of life) due to ongoing hemolysis and late anemia (7 days - 3 months of age).

Two mechanisms are attributed late anemia: “hypo-regenerative anemia” characterized by depressed erythropoiesis and “late anemia of hemolytic disease” caused by persisting antibodies, destroying young erythrocytes. “Hypo-regenerative anemia” occurs in particular in neonates treated with several IUTs as a result of bone marrow suppression. Other contributing factors for late anemia have been reported such as severity of HDFN, reduced use of exchange transfusions during the neonatal period and reduced survival of transfused red blood cells. Finally, erythropoietin deficiency is also considered as a possible contributing factor to late anemia.

Erythropoietin (EPO) has been increasingly used in full-term and particular in preterm neonates to prevent or reduce neonatal anemia without short or long-term adverse effects. Several small studies and casuistic reports suggest that neonates with HDFN may benefit from treatment with EPO to reduce the risk of delayed anemia and subsequent transfusions. However, other authors found that EPO may be less effective than expected. Due to the lack of evidence, routine use of EPO is currently not recommended. To determine a role for EPO in this group of patients, a well-designed randomized controlled clinical trial of sufficient sample size is required. Potentially, EPO stabilizes the hemoglobin levels of these infants and thus prevents anemia, hospital admissions for

transfusions and potential transfusion reactions, creating a more stable and natural postnatal course for patients with HDFN. In this scenario, the current management of weekly out-patient visits and weekly blood draws for hemoglobin level measurements, may be reduced, further contributing to reduction of the burden for these infants.

### **3. Objective**

The primary objective of this study is to investigate whether darbepoetin alfa is effective in reducing the incidence of late anemia in infants with HDFN treated with IUT and therefore in decreasing the number of postnatal transfusions per infant, compared to a control group of infants receiving standard care without darbepoetin alfa treatment.

### **4. Methods**

#### 4.1 Study population

All (near) term neonates (gestational age  $\geq 35$  weeks) with HDFN (due to D, C, c, E, Kell or other red blood cell alloimmunization) treated with IUT and admitted to the Leiden University Medical Center (LUMC) from May 2017 are eligible for the study. The LUMC is the single national referral center in the Netherlands for pregnancies complicated by maternal red blood cell alloimmunization. A prenatal national screening program in the Netherlands indicates referral to the LUMC in case of elevated antibody titers tested in maternal serum  $\geq 1/2$  in Kell immunization and  $\geq 1/16$  in D or other types of alloimmunization or in case of an elevated ADCC (antibody-dependent cell-mediated cytotoxicity) assay  $\geq 50\%$  in case of D immunization  $\geq 30\%$  in case of other blood group antigens. These pregnancies are monitored by serial Doppler measurements to assess the velocity of the middle cerebral artery (MCA), which is considered the most accurate non-invasive predictor of fetal anemia. If MCA Doppler exceeds 1.5 multiples of the median (MoM) or if signs of hydrops are present, treatment with IUT is indicated. Intrauterine transfusion is usually continued until 34-35 weeks gestation to progress these pregnancies to term. In general, labour and admission of the neonate to the Neonatology department of the LUMC is highly recommended in these pregnancies. Approximately 15 eligible patients are treated in the LUMC annually.

Postnatal anemia in this study is defined as a need for one or more erythrocyte transfusions. The LUMC transfusion guideline recommends a postnatal transfusion of 15 ml/kg irradiated erythrocytes in full-term neonates with HDFN when hemoglobin levels fall below 10.5 g/dL (6.5 mmol/L, day 0-6), below 8.9 g/dL (5.5 mmol/L, day 7-13) and below 7.2 g/dL (4.5 mmol/L, from day 14). These cut-off

values are communicated with referral hospitals after discharge from the LUMC and the research team is in contact with these hospitals to ensure transfusions are given according to these cut-off values.

#### 4.1.1 Inclusion and exclusion criteria

##### *Inclusion criteria:*

- Gestational age  $\geq$  35 weeks;
- Treatment with IUT only due red blood cell alloimmunization;
- Birth at the LUMC.

##### *Exclusion criteria:*

- Early onset proven neonatal sepsis.

#### 4.2 Study design

Randomized controlled trial without placebo. Included neonates will be randomized at birth to treatment with EPO (intervention group) or “standard care”, with 1:1 allocation, to be randomized in varying blocks of 4 and 6, no stratification is applied. In the treatment group, EPO (darbepoetin alfa) is administered subcutaneously at a dosage of 10  $\mu\text{g}/\text{kg}$  once a week, starting at approximately day 7, for a period of 8 weeks. Treatment is administered during weekly home visits in the treatment arm after discharge from the LUMC. Concomitant therapy with folate (0.25 mg/day) is given in both groups (standard practice). Concomitant iron therapy is given if ferritin level drops below 75 microg/l (standard practice). Weekly routine measurements of complete blood counts (including hemoglobin level, hematocrit and reticulocyte count) will be performed in both groups (standard practice). EPO is discontinued if hemoglobin level is  $\geq$  13 g/dL after at least 4 weeks of treatment with EPO. In EPO treated infants, blood pressure will be measured for safety reasons at onset of treatment, after four weeks and eight weeks. Monthly measurements of liver enzymes (aspartate aminotransferase (ASAT), alanine aminotransferase (ALAT), gamma-glutamyl transferase ( $\gamma$ GT) and lactate dehydrogenase (LDH)) will also be performed in all groups (standard practice). In addition, the neonatal EPO-level will be determined at birth in both groups. The number of postnatal transfusions received during the first 3 months of life and hemoglobin levels prior to the postnatal transfusion are recorded. After initial discharge from the LUMC, postnatal transfusions are recommended to be performed when hemoglobin levels fall below aforementioned cut-off values of hemoglobin.

Because of these clearly defined guideline and hemoglobin measures, blinding of caregivers to treatment allocation and use of a placebo was not deemed necessary.

Collected data, including history of pregnancy, neonatal clinical records from the initial hospitalization at the LUMC and records from additional admissions and outpatient clinic visits in other hospitals than the LUMC, were collected for each included patient with written consent of parents or caregivers. Data was upon collection blinded and entered into an online secured database (CASTOR) by a member of the research team with in this database blinding of treatment allocation. The datamanager and statistician involved are blinded as well. After all data have been collected and entered in the database, and after data cleaning and finalization of the statistical analysis plan, the database will be locked and the data will be unblinded to all parties involved.

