#### 5.10 Statistical analysis

Both intention to treat and per protocol analysis will be carried out to study the differences in outcome measures between the intervention and control group. Intention to treat analysis is our primary choice of analysis. A minimal treatment with 5 out of 8 darbepoetin injections is defined as acceptable protocol deviation. A p-value < 0.05 will be considered to indicate statistical significance. The number of top-up transfusions per infant and, the number of days of admission for top-up transfusions will be compared between both groups using a Mann-Whitney U test. The time from birth to top-up transfusion will be compared between both groups using survival analysis and a log rank test. The percentage of infants requiring a top-up transfusion up to 2 months of life, the percentage of infants with a high blood pressure and the percentage of infants with high ferritin levels will be compared between both groups using  $\chi^2$  tests. If despite randomization the groups differ at baseline in type of alloimmunization, EPO-levels at birth or treatment with exchange transfusion, a multivariable model may be used in a secondary analysis to correct for these factors.

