#### 6.3 Measurements during follow-up

Complete blood counts including hemoglobin level and reticulocyte count are determined weekly in both groups (standard practice). The number of top-up transfusions received during the first 3 months of life and hemoglobin levels prior to the top-up transfusion are recorded. Iron tests (serum iron, ferritin, transferrin and total iron binding capacity) and liver enzymes (ASAT, ALAT, YGT and LDH) will be determined monthly (standard practice). Blood pressure will be measured at the start of treatment, after four weeks and after eight weeks of treatment.

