##### *Secondary end points:*

[figure not shown]
- Number of postnatal transfusions per infant  $\geq 7$  days up to 3 months of life.
- The percentage of infants requiring a postnatal transfusion up to 3 months of life;
- Time from birth to first postnatal transfusion (days);
- Hemoglobin level at first postnatal transfusion (g/dl);
- Number of days of hospitalization and readmission(s) associated with erythrocyte transfusion(s);
- Course of hemoglobin up to 3 months of life.

*Safety end points:*

- The percentage of infants with a systolic blood pressure  $\geq 2$  SD above age adjusted mean systolic blood pressure during treatment;
- The percentage of infants with ferritin levels  $>200$   $\mu\text{g/L}$  during treatment.

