**Figure 1. Hypothesized distribution of number of postnatal transfusions**

## 5. Statistical analyses

### 5.1 Analysis sets

If after randomization parents or caregivers choose to withdraw the infant from participation before day 7, the patient will be replaced and its data excluded from all analyses.

Both intention-to-treat (ITT) and per protocol (PP) analysis will be carried out to study the differences in all outcome measures between the intervention and control group and will be presented. Intention to treat is our primary choice of analysis. The ITT analysis set consists of all randomized patients who did not withdraw before day 7, classified according to allocated treatment regardless of whether they received the assigned treatment and or any protocol deviations. Patients with major protocol deviations will be excluded from the PP analysis set. For patients assigned to the treatment arm, receiving less than 4 out of 8 darbepoetin injections is considered a major protocol violation. Furthermore, in the PP analysis patients will be classified according to treatment assignment.

If the difference between the ITT and PP analysis set is <10%, no per protocol analysis will be performed.

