### 5.2 Analysis of primary and secondary outcomes

The total number of postnatal transfusions per infant from birth to the end of the follow-up period, the number of postnatal transfusions per infant  $\geq 7$  days (which is at the start of intervention in the treatment group) and the number of days of additional admissions for postnatal erythrocyte transfusions will be compared between both groups using a Mann-Whitney U test. The time from birth to first postnatal transfusion will be compared between both groups using a log rank test and will be displayed using Kaplan-Meier survival curves (in this case transfusion-free survival) by treatment group. The period of follow-up in this study is 90 days and as such the end point for included infants that do not receive transfusions during this period, is 90 days in the survival analysis. The percentage of infants requiring a postnatal transfusion up to 3 months of life will be compared between both groups using a  $\chi^2$  test. The average or median number, depending on shape of distribution, of EPO injections in the treatment arm will be reported, as well as a summary of reasons to discontinue EPO treatment.

A multiple linear regression analysis will be performed to correct the association between treatment assignment and the primary outcome (number of postnatal transfusions). The following potential

confounders identified from previous research [unpublished data] are to be corrected for if, despite randomization, there is a baseline difference between the groups: type of alloimmunization, EPO-levels at birth, number of IUTs and treatment with exchange transfusion. In case of a non-normal distribution of the number of postnatal transfusions per neonate, log transformation will be applied. If the assumptions underlying linear regression are violated, or if the value zero occurs often, a Poisson regression will be fitted. If the number of postnatal transfusions per infant <7 days of life shows a difference between the two groups, a sensitivity analysis will be performed by performing the multiple linear regression analysis (or Poisson regression) with and without the transfusions administered <7 days. This will differentiate between the clinical course of early and late anemia and will evaluate more specifically the effect of EPO treatment, which is started at 7 days of age.

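### The protocol's between-arm test of high blood pressure has no planned control readings under the SAP, and the SAP neither records dropping it nor says how ferritin above 200 µg/L will be compared

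*SAP*

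**What the plan says.** Protocol 5.5 lists two percentages as secondary endpoints: infants with systolic pressure at least 2 SD above the age norm, and infants with ferritin above 200 µg/L, each during treatment. Protocol 5.10 states that "the percentage of infants with a high blood pressure and the percentage of infants with high ferritin levels will be compared between both groups", by chi-square.

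Protocol 6.3 times the pressure readings from the start of dosing and names no arm: "Blood pressure will be measured at the start of treatment, after four weeks and after eight weeks of treatment". SAP 4.2 names the arm: "In EPO treated infants, blood pressure will be measured for safety reasons at onset of treatment, after four weeks and eight weeks".

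Ferritin is among the monthly measurements in Protocol 6.3: "Iron tests (serum iron, ferritin, transferrin and total iron binding capacity". The list is marked as standard practice and excludes no arm.

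SAP 4.3 moves both endpoints to a safety class and keeps the window, for example "age adjusted mean systolic blood pressure during treatment". In SAP 5.2 the only chi-square sentence concerns transfusion: "The percentage of infants requiring a postnatal transfusion up to 3 months of life will be compared between both groups". Neither safety endpoint is mentioned there. SAP 5.1 says the analyses will "study the differences in all outcome measures between the intervention and control group". Table 2 gives both endpoints as n (%) with columns for each arm and for a p-value, and both rows carry a dash.

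**The concern.** A test promised in the protocol either needs data from both arms or needs to be withdrawn in writing. For blood pressure the SAP plans data in one arm only and does not say that the test is gone. Raised blood pressure is a risk of the drug named in Protocol 7.4, so a reader of the final report should be able to see why the planned comparison is absent.

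Ferritin differs, because control values should exist from routine care. Reporting the EPO arm alone would discard a randomised safety contrast that needs no extra sampling. If the arms are compared, a window defined by treatment has no meaning for infants who receive none. In the EPO arm it can also shorten, because dosing stops once hemoglobin is at or above "13 g/dL after at least 4 weeks of treatment with EPO".

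**Working it through.** The documents give no design figure for either endpoint. The 81% power in SAP 4.4 concerns transfusion counts and does not bear on this point.

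**1. Can the blood pressure test be done?** Protocol 5.10 needs a 2 × 2 table of arm by high pressure. Under SAP 4.2 the standard-care row has no planned observations. Its expected counts are zero and chi-square is undefined.

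**2. What one arm can show.** Input: 22 infants (SAP Table 2). Exact (Clopper-Pearson) 95% intervals:
- 0 of 22: upper limit 1 − 0.025^(1/22) = 15.4%, so 0 to 15.4%.
- 2 of 22 (9.1%): 1.1 to 29.2%.

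Assume that the age norm is normal and fits these infants. One reading then exceeds +2 SD with probability 0.0228. For two readings (weeks 4 and 8) the probability lies between 0.0228 if fully correlated and 1 − (1 − 0.0228)² = 0.045 if independent. With no drug effect, the chance of at least one such infant in 22 is 1 − (1 − 0.0228)^22 = 40% to 1 − (1 − 0.045)^22 = 64%. An EPO-only percentage therefore needs a label saying that it is uncontrolled.

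**3. Ferritin: size of a window effect.** With monthly tests, 8 weeks gives about two values and a stop at 4 weeks about one. Let q be the chance that a value exceeds 200 µg/L, equal in both arms, and f the share of EPO infants who stop early. Both are assumptions. If an infant's values are independent and controls have two values:
- Control percentage: 1 − (1 − q)².
- EPO percentage: f·q + (1 − f)·[1 − (1 − q)²].
- Spurious gap in favour of EPO: f·q·(1 − q).

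| q | f | Control | EPO | Gap (points) | Infants in 22 |
|---|---|---|---|---|---|
| 0.2 | 0.05 | 36% | 35.2% | 0.8 | 0.2 |
| 0.2 | 0.10 | 36% | 34.4% | 1.6 | 0.4 |
| 0.2 | 0.25 | 36% | 32% | 4 | 0.9 |
| 0.2 | 0.50 | 36% | 28% | 8 | 1.8 |
| 0.5 | 0.50 | 75% | 62.5% | 12.5 | 2.8 |

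If an infant's values are fully correlated, the gap is 0 in every row.

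**4. Ferritin: what 22 per arm can detect.** Exact power, two-sided 0.05, 80% power, assumed control rates:

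| Control rate | EPO rate needed, uncorrected chi-square | EPO rate needed, Fisher |
|---|---|---|
| 10% | 46.5% | 51% |
| 30% | 71.5% | 75.5% |
| 50% | 88% | 90.5% |

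With 5 v 5 events the risk difference is 0, with a Newcombe 95% CI of −24 to +24 points. The choice of test can matter at small counts: 4 v 0 gives p = 0.036 by uncorrected chi-square and p = 0.108 by Fisher.

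**The case against.** The strongest reply is that the SAP changed course on purpose. It schedules pressure readings in the EPO arm for safety, moves both endpoints out of the secondary class and gives them a descriptive format in Table 2. In the text copy of that table the dash falls under Standard care, which would mean EPO-only reporting. The log-rank footnote sits correctly in the p-value column, which supports that placement. The row for hemoglobin at first transfusion carries the same dash, although transfused controls would have a value, so the layout is not certain. If the dash belongs under p-value, it means that no test is planned. Both readings point away from a between-arm test.

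Most of this stands. A reader might infer that the blood pressure test was simply overlooked, or that the SAP has no method for these endpoints. The documents do not support either inference: a deliberate change is the likelier explanation, and n (%) is a reporting method. What remains is that the change from Protocol 5.10 is never stated and that SAP 5.1 still speaks of differences in all outcomes. That sentence introduces the analysis sets and specifies no test, so it is weak evidence of a planned comparison, but it leaves the intention unclear.

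A reader might also infer that the ferritin window makes EPO look safer. This is not established. It requires a between-arm comparison, which the SAP may not intend. The documents give no early-stopping rate, and SAP 5.2 expects hemoglobin to fall after birth, so frequent early stops are not evident.

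**Conclusion.** The blood pressure comparison in Protocol 5.10 cannot be done under the SAP's schedule, and the SAP should say so. This rests on the text alone. For ferritin, a comparison of randomised arms is probably available and the SAP does not say whether it will be used. That assumes the monthly standard-practice values were obtained and entered in both arms.

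A bias from unequal windows is possible but unquantified. Under the assumptions in the working it runs from 0 to 12.5 points, and with few early stoppers it is a fraction of one infant.

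The importance is minor to moderate. Adverse events are recorded (Protocol 8.2.1), the DSMB receives unblinded safety data (SAP 4.2.1), and no efficacy conclusion changes.

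**What to change.** Amend the SAP before unblinding, reconciling Protocol 5.10 with SAP 4.2, 4.3, 5.1, 5.2 and Table 2.

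1. **Blood pressure.** Withdraw the between-arm test and record this as a change from Protocol 5.10. Report the EPO-arm n (%) with an exact 95% CI, labelled uncontrolled, and show the onset reading separately from weeks 4 and 8.
2. **Ferritin.** Report the proportion with any value above 200 µg/L in both arms over one common post-baseline age window, about day 7 to day 63 (the stated start plus 8 × 7 = 56 days), regardless of when EPO stopped. Give the number of values per infant by arm and the risk difference with 95% CI. A p-value is optional. If one is given, name the test beforehand; an exact test is preferable when counts are small.

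The cost is about one paragraph and some table labels. No new sampling is needed if routine ferritin values were entered. SAP 4.2 places SAP finalization before database lock and unblinding, but the documents do not show whether that point has passed. If it has, the change should be labelled as made afterwards.

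There are drawbacks. Blood pressure stays descriptive. The fixed window includes off-treatment time in early stoppers, which may dilute a true drug effect. Because dosing starts at approximately day 7, a pre-dose value could fall inside the window. At 22 per arm only large ferritin differences are detectable.
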